## **Outcome measures**

### ***Anamnestic Information***

The anamnestic information collected for each participant will include age, age at diagnosis of scoliosis, the amount of motor therapy interventions received, and the type of genetic mutation (see data collection sheet in Appendix 4).

### ***Rett syndrome severity level***

The Rett Assessment Rating Scale (see RARS form in Appendix 5) will be used to evaluate the severity of RTT clinical manifestation at T1. The RARS is a 31-items RTT-specific severity scale.[41] Each item concerns a specific phenotypic RTT characteristic. The

total score indicates the participant's RTT severity level ranging from a mild deficit (reflected by lower scores) to severe symptoms (reflected by higher scores). A standardization procedure for the Italian population with RTT was conducted for the RARS. Skewness and kurtosis values, calculated for the total score distribution, were 0.110 and 0.352, respectively. The distribution was found to be normal. Internal consistency for the total score (0.912), as well as for the subscales, was high (0.811–0.934).[41,42]

### ***Scoliosis Progression***

The progression of scoliosis will be assessed during the study by measuring Cobb's angle on three anteroposterior X-rays of the spine collected respectively at T1, T2, and T3. The girl will be positioned in the most upright position comfortable for her. The angle will be measured using standard procedures. If the participant has an X-ray examination of the spine carried out in the manner prescribed for this study in the six months prior to the start of the intervention, this radiograph will be used as a pre-intervention examination. If the participant does not have an x-ray examination with the characteristics described above, it will be carried out as part of this project in compliance with the international guidelines for the management of scoliosis in RTT, which provide for the carrying out of six-monthly radiographic examinations in the presence of evolving scoliosis.[12] Moreover, the radiographic examinations carried out periodically by the participants before the recruitment at the participants' reference hospitals will be collected by the researchers to allow the extraction of data relating to the evolutionary trajectory of scoliosis up to the time of recruitment. The Cobb's angle will be obtained from the average value of three measurements carried out by independent blinded (to the treatment status of each subject) medical specialists with clinical experience concerning scoliosis in RTT. Using the results provided by different clinicians blinded to the procedure, the date of the x-ray is taken, and the functional state of each participant will allow a more reliable final measurement.[43]

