## **Inclusion Criteria**

- Diagnosis of RTT with confirmed MECP2 gene mutation;[40]
- Diagnosis of unstructured flexible scoliosis (Cobb angle between  $10^\circ$  and  $40^\circ$ ) measured radiologically with an x-ray performed no more than six months before the recruitment;
- Age between 6 and 16 years.

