## **Study Protocol**

The participants' parents will receive an information sheet regarding the study and informed consent for participation and collection of video materials at the recruitment. A reference telephone number and an e-mail address will be provided to be contacted in case they would like further information or would like to communicate the exit from the study. The eligibility of the candidates will be assessed at the time of recruitment (T1) through an initial neurological or physiatrist evaluation. At the same time, each participant will undergo a rehabilitation evaluation to collect the outcome measures (see section "Data collection") and create an individualized intervention plan specific to the participant's scoliosis, functional abilities, and parental/educational setting's availability. During the evaluation, the postural needs of the participants will also be identified, and a qualified technician will build or adjust the positioning devices, making them suitable for each intervention plan. Using block randomization, participating girls will be randomly divided into treatment (Group 1) or delayed treatment (Group 2) groups. Participants in Group 1 will begin carrying out the rehabilitation program immediately after the first assessment session (T1). Each program will require the daily performance of different postures and therapeutic activities at the girls' educational facilities and homes, based on the availability of families, for a duration of 10 months. Specific strategies that will be implemented will include maintaining asymmetrical postures that oppose the scoliosis curve during activities and exercises in sitting, standing, and walking positions (according to each participant's functional abilities). These strategies refer to a hypercorrective postural positioning of scoliosis. In addition, activities involving weight bearing on the lower limbs, such as walking and standing for at least two hours a day, will be encouraged, and passive stretching and spinal mobilization exercises will be conducted.

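### The positioning rule for the spine X-rays does not require the same posture at T1, T2 and T3 or have it recorded, so part of a measured Cobb change could reflect posture rather than progression

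*Combined protocol and SAP*

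**What the plan says.** The Cobb angle comes from "three anteroposterior X-rays of the spine collected respectively at T1, T2, and T3". On how the film is taken, the Scoliosis Progression section specifies only the anteroposterior view and this rule: "The girl will be positioned in the most upright position comfortable for her". It names no posture (standing, sitting or lying), no level of support and no corset status.

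An existing film can serve as the pre-intervention film on this condition: "If the participant has an X-ray examination of the spine carried out in the manner prescribed for this study in the six months prior". The manner prescribed is the same comfort-based rule.

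Two safeguards follow. On measurement: "The angle will be measured using standard procedures". And the value used is "the average value of three measurements carried out by independent blinded (to the treatment status of each subject) medical specialists", who are also to be unaware of the film date and the girl's functional state.

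Three other sections bear on the point:

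- Inclusion Criteria: "Diagnosis of unstructured flexible scoliosis", with a Cobb angle of 10° to 40°.
- Study Protocol: the programme uses hypercorrective positioning and exercises in sitting, standing and walking, and "activities involving weight bearing on the lower limbs, such as walking and standing for at least two hours a day, will be encouraged".
- Statistical analysis: between-group comparisons are to be adjusted for age and gross motor skills. X-ray position is not mentioned.

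**The concern.** How upright a girl can comfortably be depends on her function at the time. The programme works on sitting, standing and walking, and at T2 Group 1 has completed it while Group 2 has not. If comfortable posture changes between films, and changes differently in the two groups, the T1-T2 comparison of Cobb change contains a posture component. That component arises after randomisation, so randomisation does not balance it. Flexible curves are the kind for which position and support on the day could plausibly matter.

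Cobb change is the measure on which the efficacy question and the sample size rest. If film conditions are not recorded when the films are taken, it may be impossible later to tell how much of an observed difference could be due to posture.

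**Working it through.** **Do the existing safeguards reach the problem?**

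| Provision | What it controls | What it leaves open |
|---|---|---|
| Standard procedures for the angle | How the angle is drawn | How the girl was placed |
| Three averaged blinded readings | Reading error and reader expectation | Posture already on the film |
| Existing T1 film must follow the study manner | Rules out films taken in another manner | That manner fixes no posture |
| Adjustment for gross motor skills | Part of the difference in function between girls | Position on each film; the visit whose motor score is used is not stated |
| Exclusion of corset use for most waking hours | Heavy corset users | Part-time users remain eligible |
| Appendix 4 intake sheet | Corset type and hours, walking support, date of last spine film | Conditions under which any film was taken |

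None of these requires the T1 position to be repeated, and none records position on the film.

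**How large could the effect be?** The plan gives no figure for posture, so there is none to reproduce.

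Inputs from the plan: SD 8° (from the 14 ± 8° per year in Sample Size and Power Calculation) and 10 girls per group.

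Assumptions, not in the documents: a change of position shifts the measured angle by 5° to 10°, and 1 to 3 of the 10 girls in one arm change position in the same direction with no offset in the other arm.

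Step 1. Shift in the arm mean = (girls changed / 10) × posture effect.

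- 1 girl: 1/10 × 5° = 0.5°; 1/10 × 10° = 1.0°
- 3 girls: 3/10 × 5° = 1.5°; 3/10 × 10° = 3.0°

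Step 2. Standard error of the between-group difference = SD × √(2/n) = 8 × √(2/10) = 3.6°. The largest shift is 3.0/3.6 = 0.8 of a standard error and the smallest is 0.5/3.6 = 0.1. The SD is for a yearly change. If it shrank in proportion to 10 months (8 × 10/12 = 6.7°), the standard error would be 6.7 × √(2/10) = 3.0°, and the largest shift would be about one standard error.

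Step 3. Rejection rate of a two-sided 0.05 t-test when the true effect is zero (noncentral t, 18 degrees of freedom, SD 8°, 10 per arm):

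| Between-arm posture shift | Rejection rate |
|---|---|
| 1° | 6% |
| 2° | 8% |
| 3° | 12% |

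Step 4. If posture instead adds random error of SD s to each film, unrelated to group, the SD of change is √(64 + 2s²), where 64 = 8². The difference detectable with 80% power is that SD × √(2/10) × (1.96 + 0.84).

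| s per film (assumed) | SD of change | Detectable difference |
|---|---|---|
| 0° | 8.0° | 10.0° |
| 2° | 8.5° | 10.6° |
| 5° | 10.7° | 13.4° |

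**The case against.** The strongest reply is that the rule is the same for every girl and every visit. A girl whose function is stable would probably be filmed the same way each time, and a comfort-based rule is understandable in children with severe motor impairment. That stands: the plan fails to require a constant posture, but nothing in it shows that posture will change.

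The partial safeguards also count. An existing film must have been taken in the study's manner, heavy corset users are excluded, and motor function is measured and adjusted for. These narrow the problem without closing it, as the table above shows.

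A reader might infer a direction, for example that a trained girl newly filmed upright would look worse. The documents do not support this. A more upright, loaded position could raise the angle, while better trunk control could lower it, so either a false or a missed effect is possible.

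A reader might also set the shift against the 2° gap between 14° and 12° in Sample Size and Power Calculation. That gap is not a between-group target. The text asks for a mean increase below 12° in both groups after the programme, and 14° is a yearly figure, which pro rata is 14 × 10/12 = 11.7° over 10 months. The standard error of the difference is the better yardstick, and against it the assumed shifts are modest.

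**Conclusion.** The gap is real. The stated rule ties film posture to current function, the programme is meant to alter that function, and nothing in the plan repeats, records or adjusts for position on the film. A posture contribution to Cobb change, possibly differing by group at T2, cannot be ruled out as the plan stands.

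Size and direction are unknown. Under the stated assumptions the shift is at most about one standard error of the between-group difference, enough to raise the false rejection rate from 5% to about 12% at the top of the range and hardly at all at the bottom. Both the 5-10° effect and the 1 to 3 girls are assumptions. The text does not support a conclusion that the Cobb comparison will be biased, or in a particular direction. The point is worth acting on because the remedy is cheap and film conditions may not be recoverable afterwards.

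**What to change.** 1. For every film, including any pre-study film used as T1, record position (standing, sitting or lying), external support, and corset on or off. Enter unknown where a pre-study film does not show it.
2. Take the T2 and T3 films in the T1 position and with the T1 support where the girl can still hold them.
3. Keep all girls in the main Cobb analysis. Flag film pairs whose conditions differ or are unknown, and report their number by group.
4. Give a same-position analysis only as a supportive check, and state its limit: it selects on function after randomisation, which the programme may affect, in arms of only 10.

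The cost is one line in the radiography instruction, three fields on the form and a small extra analysis. Some pre-study films will stay of unknown condition, and girls who lose function may remain unmatched, but the counts by group will show how many. Existing films are still accepted as T1, so no extra X-rays are needed.

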## **Sample Size and Power Calculation**

The information available in the literature suggests that the Cobb angle in RTT typically increases by approximately  $14 \pm 8^\circ$  Cobb per year. Based on these data, an alpha of 0.05 and a beta of 0.8, we estimate that for this study, the researchers will need a sample size including two groups of 10 subjects and that statistical significance will be achieved if both groups of participants will show an average increase in the scoliotic curve of less than  $12^\circ$  Cobb after the implementation of the proposed program.

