### ***Adherence to the Program***

The compliance with the intervention will be measured through the smartphone application. This will allow an assessment of the amount of treatment received, which is essential for calculating the correlation between the number of therapeutic activities performed and the variation of Cobb's angle.

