### **Statistical analysis**

The normality of each variable's distribution will be assessed using the Shapiro-Wilk normality test. The ages, amount of received physical rehabilitation interventions, scoliotic curve degrees, behavioral characteristics, and activity and gross motor functional levels obtained at T1 will be compared between the two groups to assess their comparability through Wilcoxon's signed-rank test or Student's T-test (dependent of the variable distribution characteristics). Changes that occurred in the variables of each group at T1, T2, and T3 will be evaluated with Friedman's test or with the repeated measure ANOVA (dependent on the variable distribution characteristics). Between groups comparison for each variable collected at T1, T2, and T3 and for their variations that occurred between T1 and T2 and between T2 and T3 will be conducted using the Wilcoxon's signed-rank test or Student's T-test (dependent of the variable distribution characteristics), applying an appropriate adjustment for the age and gross motor skills of the participants. Relations will be searched between variables collected at T1 and the changes in the scoliosis curve degree and motor functioning after the treatment using Spearman's rank correlation coefficient or Pearson's correlation coefficient (dependent on the variable distribution characteristics). Moreover, a relation between the compliance with the proposed program and the changes in the scoliosis curve degree and motor functioning after the treatment will be searched using the Spearman's rank correlation coefficient or Pearson's correlation coefficient (dependent on the variable distribution characteristics). The threshold for significance of the above-described analyses will be set at  $\alpha = 0.05$ . No correction for multiple comparisons will be applied.[48]

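### A baseline film up to six months old lets the T1-T2 Cobb change cover 10-16 months against about 10 for T2-T3, and the analysis takes no account of elapsed time.

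*Combined protocol and SAP*

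**What the plan says.** All references are to the combined protocol and SAP.

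- **Baseline film.** Scoliosis Progression plans three X-rays, at T1, T2 and T3. If a conforming film was taken "in the six months prior to the start of the intervention, this radiograph will be used as a pre-intervention examination". A new film is made only when no such film exists. Inclusion Criteria also allows a six-month-old film, but counts the six months back from recruitment.
- **Timing.** In Study Protocol, recruitment is T1, Group 1 starts directly after it, T2 for everyone is 10 months after that start, and T3 follows a second 10-month period in which Group 2 is treated.
- **Within-group analysis.** "Changes that occurred in the variables of each group at T1, T2, and T3 will be evaluated with" Friedman's test or repeated-measures ANOVA.
- **Between-group analysis.** Values and changes are compared, "applying an appropriate adjustment for the age and gross motor skills of the participants".
- **Correlations.** "Relations will be searched between variables collected at T1 and the changes in the scoliosis curve degree and motor functioning after the treatment". The plan also seeks "a relation between the compliance with the proposed program and the changes in the scoliosis curve degree". Adherence to the Program calls the amount of treatment received "essential for calculating the correlation between the number of therapeutic activities performed and the variation of" the Cobb angle.
- **Earlier films.** Routine hospital films are gathered for "extraction of data relating to the evolutionary trajectory of scoliosis up to the time of recruitment", but Statistical analysis plans no use of them.

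No film date, interval between films or per-month change enters any analysis.

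**The concern.** In a progressive deformity, the change between two films depends on the time between them. An archived T1 film adds up to six months of untreated progression to T1-T2 and nothing to T2-T3.

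For Group 2, T1-T2 is the waiting period and T2-T3 the treated period, so the extra time makes waiting look worse and treatment look better. For Group 1, T1-T2 is the treated period, so the extra time makes its treated change look larger. An equal true effect would then look weaker in Group 1 than in Group 2.

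The plan does not define the post-treatment change used in the correlations. If it is T1-T2 for Group 1 and T2-T3 for Group 2, some changes include untreated lead-in and others do not.

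The two six-month windows also differ in anchor. For Group 1, recruitment and start of intervention coincide. For Group 2, the start of intervention comes after T2.

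**Working it through.** The plan gives no figure for the interval between films, so there is none to reproduce. The sample-size statement does not bear on this point.

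**Inputs from the documents.** Film age 0-6 months; 10-month periods; 10 girls per group; baseline 10-40°. Sample Size and Power Calculation: "The information available in the literature suggests that the Cobb angle in RTT typically increases by approximately" 14 ± 8° per year. Introduction: a radiographic cohort of 128, rising 0.438 per year on the square-root scale.

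**Assumptions.** A share p of girls have an archived film with age uniform over 0-6 months (mean 3); the others have fresh films. Reading error has SD 2°. Progression follows independent increments or constant individual rates; paired results are given in that order.

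**1. Interval.** T1-T2 = 10 + (0 to 6) = 10 to 16 months; T2-T3 = about 10.

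**2. Excess at 14° per year.** Maximum 14 × 6/12 = 7.0°. Mean 14 × 3p/12 = 0, 1.75 or 3.5° for p = 0, 0.5 or 1.

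**3. Apparent slowing in Group 2 with no effect.** 1 − 10/(10 + 3p) = 0, 13% or 23%.

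**4. Cohort rate.** Gain over m months from baseline b is (√b + 0.438m/12)² − b. All archived is taken at the mean film age, so 13 months and then 10:

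| Baseline | Excess at 3 (6) months | All archived: first 13, next 10 months | Slowing | All fresh: first 10, next 10 months | Acceleration |
|---|---|---|---|---|---|
| 10° | 0.70° (1.43°) | 3.23°, 2.79° | 14% | 2.44°, 2.71° | 11% |
| 25° | 1.11° (2.24°) | 4.97°, 4.13° | 17% | 3.78°, 4.05° | 7% |
| 40° | 1.40° (2.82°) | 6.23°, 5.10° | 18% | 4.75°, 5.02° | 6% |

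**5. A paired waiting-versus-treated t test in Group 2, if one were run.** Simulated rejection of a true null at 14° per year (20,000 trials): 5.2/5.1% with fresh films, 6.8/13.0% at p = 0.5, 12.5/39.9% at p = 1. Change per month at p = 1 restores 4.9/4.9%. At the cohort rate with p = 1, rejection is about 5-10%, with annual SDs of 2-8° assumed.

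**6. Randomised T1-T2 comparison.** Simulated type I error at p = 1 is 5.1/5.0%. The SD of change rises:

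- independent increments: √(64 × 10/12) = 7.30° to √(64 × 13/12 + 2.02²) = 8.57°;
- constant rates: 8 × 10/12 = 6.67° to √(64 × 172/144 + 196 × 3/144) = 8.97°.

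Reading error adds 2 × 2² = 8 to each variance, giving 7.83° to 9.02° and 7.24° to 9.41°. If the programme halves progression, the effect is 11.67/2 = 5.83°, taken as a shift in the mean. Effect over standard error, 5.83/(SD × √(2/10)), falls from 1.67 to 1.45 and from 1.80 to 1.39. Power falls from about 35-39% to 26-28%.

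**7. Treated change in the two groups, same scenario.** Group 1 T1-T2: 3.5 + 5.83 = 9.3°. Group 2 T2-T3: 5.8°.

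**8. Compliance correlation, same interval reading, p = 1, true r = −0.50 (assumed).** Simulated pooled r moves from about −0.45 to −0.39 to −0.41. Group 1 alone moves from −0.44 to −0.35 to −0.39. For scale, the sampling SD (1 − r²)/√(n − 1) is 0.80/√19 = 0.18 for 20 girls and 0.81/√9 = 0.27 for 10. With true r = 0 and equal compliance in both groups, rejection stays at 4.7-4.8%.

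**The case against.** The strongest reply is that the named between-group tests are sound. Randomisation balances film age in expectation at T1-T2, and T2-T3 is about 10 months in both arms. A reader might infer that the randomised result is biased. It is not; its cost is precision.

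A reader might also infer that the plan contains a test with up to 40% false positives. It does not. The within-group analysis is an omnibus test of levels, and no paired waiting-versus-treated test is named. The high rates apply only if one is added and progression is near 14° per year; at the cohort rate they are close to nominal. The risk lies in reading or following up Group 2's pattern as slowing, which a waiting-list design invites.

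Nor do the documents show that Group 2 would appear to slow without any effect. That needs enough archived films, and neither their share nor their ages are given. Films not taken as the study prescribes do not qualify.

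The dilution of the correlations is small against sampling error at 10-20 girls and rests on one reading of an undefined change. Motor scores are taken at the visits and are unaffected.

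On the anchor, a reader might take the wording to let Group 2's T2 film be six months old. Intervals would then differ by arm and the randomised contrast would not be safe. But Study Protocol and Scoliosis Progression place measurement at T2 for all, so this calls for clearer wording and does not establish a bias.

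**Conclusion.** The concern holds for comparisons across periods and for analyses that use Group 1's T1-T2 change as its treated change. The permitted interval of 10-16 months against about 10 follows directly from the text, as does the lack of any elapsed-time term.

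The size depends on the unknown share of archived films. With no treatment effect, Group 2's apparent slowing is 0-23% at 14° per year. At the cohort rate it runs from 6-11% acceleration to 14-18% slowing, so film age can reverse the direction of the pattern. The mean excess with all films archived is 3.5° at the planning rate and 0.7-1.4° at the cohort rate. The correlations are at most modestly diluted.

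The randomised T1-T2 comparison keeps its type I error. Its loss of power, from about 35-39% to 26-28%, assumes 14° per year, halved progression, all films archived with uniform age, and a 2° reading error.

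**What to change.** 1. Reconcile Inclusion Criteria with Scoliosis Progression: anchor the six-month window to T1 (recruitment) in both groups, and state that the T2 and T3 films are those taken at those visits.
2. Record the date of every film for the analysis. The readers stay blinded to it.
3. In the within-group, cross-period, baseline-predictor and compliance analyses of Cobb angle, use actual film-to-film time. For Group 2, express the waiting and treated changes per month, since each interval is wholly untreated or wholly treated. For Group 1, state that T1-T2 includes untreated lead-in and add a sensitivity analysis. This either subtracts film age times an assumed untreated rate, shown over a range from the cohort rate to the Introduction's 14-21° per year, or is limited to girls with a recent T1 film.
4. Leave the randomised T1-T2 comparison as planned and report film age by arm. Dividing by the interval would shrink the estimated effect, because the lead-in is untreated: under uniform film age the factor is (10/6) × ln(1.6) = 0.78.

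A model with separate slopes for untreated, treated and app-only months is not requested; 20 girls with three films each would hardly support it.

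The cost is SAP wording and a dates field; the Appendix 4 sheet already asks for the date of the last spine film. The changes assume roughly linear progression over the interval and bring no gain to the randomised contrast.
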